6.4.4 Reporting of serious adverse events

All SAEs have to be reported, whether or not considered causally related to the investigational product, or to the study procedure(s). All SAEs will be recorded in the eCRF.

If any SAE occurs in the course of the study, then investigators or other site personnel inform appropriate AstraZeneca representatives immediately, or **no later than 24 hours** of when he or she becomes aware of it.

The designated AstraZeneca representative works with the investigator to ensure that all the necessary information is provided to the appropriate AstraZeneca patient safety data entry site within **one calendar day** of initial receipt for fatal and life threatening events and within **five calendar days** of initial receipt for all other SAEs.

For fatal or life-threatening adverse events where important or relevant information is missing, active follow-up is undertaken immediately. Investigators or other site personnel inform AstraZeneca representatives of any follow-up information on a previously reported SAE immediately, or **no later than 24 hours** of when he or she becomes aware of it.

Once the investigators or other site personnel indicate an AE is serious in the WBDC system, an automated email alert is sent to the designated AstraZeneca representative.

If the WBDC system is not available, then the investigator or other study site personnel reports aSAE to the appropriate AstraZeneca representative by telephone.

The AstraZeneca representative will advise the investigator/study site personnel how to proceed.

The reference document for definition of expectedness is Section 5.4 of the Investigators' Brochure for AZD9291.

6.5 Pharmacokinetics

6.5.1 Collection of pharmacokinetic samples

Venous blood samples for determination of concentrations of AZD9291 and its metabolites (AZ5104 and AZ7550) in plasma will be taken at the times presented in Table 4. Discussions will be required with the AZ PK representative as to any effect on the PK sample schedule if dose interruption occurs within 3 days of PK sampling. The date and time of collection of each sample and the date and time of dose will be recorded.

Time relative to Dose	Single Dosing Cycle 0						ple Dos	Multiple Dosing Cvcle 2			
	D1	D2	D3	D4	D6	D1	D8	D9 (pre- dose)	D15 (pre- dose)	D1	D2 (pre- dose)
Pre-dose	X					X	X		Х	X	
0.5h	X						X				
1h	X						Х			X	
1.5h	X						Х			X	
2h	Х						Х			Х	
3h	Х						Х				
4h	X						Х			X	
6h	X						Х			X	
8h	X						Х			Х	
10h	X						X			X	
12h	X						Х			X	
24h		Х						X			Х
48h			X								
72h				X							
120h					X						

Table 4PK blood sample schedule

A 5 min window will be allowed for samples taken at 1h; a 10 min window for samples taken at 1.5-10h; a 1h window for samples taken at 12h and 24h, a 2h window at 48h-72h and a 24h window at 120h.

The timing of the pharmacokinetic samples may be adjusted during the study, dependent on emerging data, in order to ensure appropriate characterisation of the plasma concentration time profiles. The total number of samples and the total volume of blood taken from each patient will not exceed that detailed in Section 6.6.1. Residual samples may be analysed for exploratory biomarkers.

Samples will be collected, labeled, stored and shipped as detailed in the Laboratory Manual.

6.5.2 Determination of drug concentration in pharmacokinetic samples

Samples for determination of AZD9291 (and metabolite) concentrations in plasma will be analysed by on behalf of AstraZeneca, using an appropriate bioanalytical method. Full details of the analytical method used will be described in a separate bioanalytical report.

All samples still within the known stability of the analytes of interest (ie, AZD9291 and its metabolites AZ5104 and AZ7550) at the time of receipt by the bioanalytical laboratory will be analysed.

In addition, the pharmacokinetic samples may be subjected to further analyses by AstraZeneca in order to further investigate the presence and/or identity of additional drug metabolites. Any results from such analyses will be reported separately from the Clinical Study Report.

Details on sample processing, handling, shipment and storage are provided in the Laboratory Manual.

6.6 Biological sampling procedures

6.6.1 Volume of blood

The number of samples taken, as well as the volume required for each analysis, may be changed during the study as new data on AZD9291 become available. The estimated total volume of blood that will be drawn from each subject in this study is as follows.

Assessment		Sample volume ^(a) (mL)	No. of samples ^(b)	Total volume (mL)
Safety	Clinical chemistry	5	9	45
	Haematology	2	9	18
Pharmacokinetics		2	39	78
Serum β -HCG ^(c)		4	1	4
Total				145

(a) The sample volume for safety assessments, serum β-HCG are approximate volumes that refers to sitespecific change.

(b) Number of samples is estimated based on patients onaverage completing 4 cycles.

(c) Only for pre-menopausal women.

Safety laboratory assessments will be performed locally at each centre's laboratory by means of their established methods. The number of samples/blood volumes is therefore subject to site-specific change.

6.6.2 Handling, storage and destruction of biological samples

The samples will be used up, or disposed of after analyses or retained for further use as described below.

Any pharmacokinetic sample remaining after analysis for AZD9291 and its metabolites may be used for EGFR gene mutation detection as exploratory biomarker analyses. These analyses are for AstraZeneca use only and will not be included in the CSR.

Biological samples for future research will be retained at AstraZeneca or it's designee for a maximum of 15 years following the finalisation of the Clinical Study Report. The results from future analysis will not be reported in the Clinical Study Report but separately in a bioanalytical method validation report.

6.6.2.1 Pharmacokinetic samples

Incurred sample reproducibility analysis, if any, will be performed alongside the bioanalysis of the test samples and reported in a separate bioanalytical report.

Key samples for metabolite identification and/or analysis will be retained at on behalf of Drug Metabolism and Pharmacokinetics (DMPK), AstraZeneca for a maximum of one year following the finalisation of the Clinical Study Report. The results from the investigation will not be reported in the Clinical Study Report but separately in a DMPK report.

6.6.3 Labelling and shipment of biohazard samples

The Principal Investigator ensures that samples are labeled and shipped in accordance with the Laboratory Manual and the Biological Substance, Category B (materials containing or suspected to contain infectious substances that do not meet Category A criteria), see Appendix C of this Clinical Study Protocol 'IATA 6.2 Guidance Document'.

Any samples identified as Infectious Category materials should not be shipped and no further samples taken from the patient unless agreed with AstraZeneca and appropriate labelling, shipment and containment provisions are approved.

All archival tumour samples should be shipped at ambient temperature as per the Laboratory Manual to the AstraZeneca designated central Contract Research Organisation.

6.6.4 Chain of custody of biological samples

A full chain of custody is maintained for all samples throughout their lifecycle.

The Principal Investigator at each centre keeps full traceability of collected biological samples from the patients while in storage at the centre until shipment or disposal (where appropriate) and keeps documentation of receipt of arrival.

The sample receiver keeps full traceability of the samples while in storage and during use until used or disposed of or until further shipment and keeps documentation of receipt of arrival.

AstraZeneca keeps oversight of the entire life cycle through internal procedures, monitoring of study sites and auditing of external laboratory providers.

Samples retained for further use are registered in the AstraZeneca biobank system during the entire life cycle.

6.6.5 Withdrawal of informed consent for donated biological samples

If a patient withdraws consent to the use of voluntarily donated biological samples, then the samples will be disposed of/destroyed, and the action documented. If samples are already analysed, AstraZeneca is not obliged to destroy the results of this research. The patient may continue in the study.

The Principal Investigator:

- Ensures AstraZeneca is notified immediately of the patient's withdrawal of informed consent to the use of donated biological samples
- Ensures that biological samples from that patient, if stored at the study site, are immediately identified, disposed of/destroyed, and the action documented
- Ensures the laboratory (ies) holding the samples is/are informed about the withdrawn consent immediately and that samples are disposed of/destroyed, the action documented and the signed document returned to the study site
- Ensures that the patient and AstraZeneca are informed about the sample disposal

AstraZeneca ensures the central laboratory (ies) holding the samples is/are informed about the withdrawn consent immediately and that samples are disposed of/destroyed, the action documented and the document returned to the study site.

6.7 Anti-tumour activity

6.7.1 Tumour assessments

RECIST 1.1 guidelines for measurable, non-measurable, target lesions (TLs) and non-target lesions (NTLs) and the objective tumour response criteria are presented in Appendix F of this Clinical Study Protocol.

Baseline CT or MRI assessments of chest and abdomen (including liver and adrenal glands) must be performed no more than 28 days before the start of study treatment, and ideally should be performed as close as possible to the start of study treatment. Additional imaging may be performed based on individual patient signs and symptoms. CT/MRI scan of the brain should be performed in patients with known or suspected brain metastases. The methods of assessment used at baseline should be used at each subsequent follow-up assessment.

Follow-up assessment should be performed every 6 weeks (\pm 7 days) up to and including progression (corresponding with the RECIST assessments – and continuing after treatment discontinuation in the absence of disease progression).

Any other sites at which new disease is suspected should also be appropriately imaged. If an unscheduled assessment is performed and the patient has not progressed, every attempt should be made to perform subsequent assessments at the scheduled visits whilst the patient remains on study treatment.

Categorisation of objective tumour response assessment will be based on the RECIST 1.1 guidelines for response: CR (complete response), PR (partial response), SD (stable disease) and PD (progression of disease). Target lesion progression will be calculated in comparison to when the tumour burden was at a minimum (ie, smallest sum of diameters previously recorded on study). In the absence of progression, tumour response (CR, PR, SD) will be calculated in comparison to the baseline tumour measurements obtained before starting treatment.

If the investigator is in doubt as to whether progression has occurred, particularly with response to NTLs or the appearance of a new lesion, it is advisable to continue treatment and reassess the patient's status at the next scheduled assessment or sooner if clinically indicated. If repeated scans confirm progression, then the date of the initial scan should be declared as the date of progression.

To achieve 'unequivocal progression' on the basis of non-target disease, there must be an overall level of substantial worsening in non-target disease such that, even in presence of SD or PR in target disease, the overall tumour burden has increased sufficiently to merit discontinuation of therapy. A modest 'increase' in the size of one or more NTLs is usually not sufficient to qualify for unequivocal disease progression status.

It is important to follow the assessment schedule as closely as possible. Please refer to the study plan in Section 6.1 and Appendix F, Section4.1.

All RECIST 1.1 assessment images will be reviewed at site.

7. EVALUATION AND CALCULATION OF VARIABLES AND STATISTICAL METHODS

7.1 **Definition of study endpoints**

To meet the objectives for this study, data for the following endpoints will be collected:

Primary endpoints

- PK exposure parameters derived from plasma concentrations of AZD9291, and metabolites AZ5104 and AZ7550
- Following the single dose part (or first dose) of the study

Maximum plasma concentration (C_{max}), time to C_{max} (t_{max}), terminal rate constant (λz), terminal half life ($t_{\lambda\lambda z}$), area under the plasma concentration-time curve from zero to 24 hours (AUC₍₀-

 $_{24)}$), from zero to 72 hours (AUC₍₀₋₇₂₎), from zero to the time of the last measurable concentration (AUC(0-t)) and from zero to infinity (AUC), apparent plasma clearance (CL/F) (AZD9291 only), apparent volume of distribution (AZD9291 only), mean residence time (MRT), where possible.

• Following the multiple dose part of the study:

Cycle 2 Day 1

Maximum plasma concentration at steady state ($C_{ss max}$), time to $C_{ss max}$ ($t_{ss max}$), minimum plasma concentration at steady state ($C_{ss min}$), area under the plasma concentration-time curve from zero to the end of the dosing interval (AUCss), apparent plasma clearance at steady state (CL_{ss}/F) (AZD9291 only), extent of accumulation on multiple dosing (R_{AC}), time dependency of the pharmacokinetics where possible.

Cycle 1 Day 8

 C_{C1D8} max, t $_{C1D8}$ max, C_{C1D8} min, AUCtau.

Trough concentrations on Cycle 1 Day 8, day 15 and Cycle 2 day 1.

• The ratio of metabolite to AZD9291 will also be calculated.

Secondary endpoints

- Safety and Tolerability-AEs (both in terms of MedDRA preferred terms and CTCAE grade)
- Physical examination, WHO performance status, vital signs including pulse and blood pressure, 12 lead ECGs, echocardiogram/MUGA (for LVEF), haematology, clinical chemistry, urinalysis, concomitant medications.
- Tumour response including objective response.
- Safety endpoints are defined in Section 6.4. Derivations, calculations and analysis plans for each of these endpoints are presented below.

7.2 Determination of sample size

The primary objective of this study is to characterise the pharmacokinetics (PK) of AZD9291 after a single then multiple oral doses of AZD929. The key secondary objective is to investigate the safety and tolerability of AZD9291 to recommend dose(s) for evaluation in future clinical studies. Hence the number of patients in the cohorts has been based on the desire to obtain adequate tolerability, safety and pharmacokinetic data while exposing as few patients as possible to the investigational product and procedures. Tumour response as measured using RECIST 1.1 will be assessed to provide preliminary anti-tumour activity in targeted patient population.

Approximately 12 patients with advanced NSCLC will be enrolled in each cohort

7.3 Calculation or derivation of safety variables

Safety and tolerability will be assessed in terms of AEs, physicial examination, laboratory data, vital signs, ECG and echocardiogram/MUGA (for LVEF) changes. These will be collected for all patients. Appropriate summaries of these data will be presented as described in Section 7.7.

ECG Changes

QTc will be calculated by AstraZeneca using both Bazett's and Fridericia's formulae.

Creatinine Clearance

Estimated creatinine clearance will be calculated using the Cockcroft and Gault formula.

7.3.1 Other significant adverse events

During the evaluation of the AE data, an AstraZeneca medically qualified expert will review the list of AEs that were not reported as SAEs and AEs leading to discontinuation of investigational product. Based on the expert's judgement, adverse events of particular clinical importance may, after consultation with the Global Safety Physician, be considered other significant adverse events (OAEs) and reported as such in the Clinical Study Report. A similar review of laboratory values, vital signs, ECGs and other safety assessments will be performed for identification of other significant adverse events.

Examples of these are marked haematological and other laboratory abnormalities, and certain events that lead to intervention (other than those already classified as serious), dose reduction or significant additional treatment.

7.4 Calculation or derivation of pharmacokinetic variables

Pharmacokinetic analysis of the plasma concentration data for AZD9291 and its metabolites will be performed by Quantitative Clinical Pharmacology, Alderley Park, AstraZeneca or delegate on behalf of Quantitative Clinical Pharmacology. The actual sampling times will be used in the parameter calculations and PK parameters will be derived using standard non-compartmental methods.

Where possible the following PK parameters will be determined for AZD9291, AZ5104 and AZ7550.

Following the single dose part (or first dose) of the study:

Maximum plasma concentration (C_{max}), time to C_{max} (t_{max}), terminal rate constant (λ_z), terminal half life ($t_{\frac{1}{2}\lambda_z}$), area under the plasma concentration-time curve from zero to 24 hours (AUC₍₀₋₂₄₎), from zero to 72 hours (AUC₍₀₋₇₂₎), from zero to the time of the last measurable concentration (AUC_(0-t)) and from zero to infinity (AUC), apparent plasma clearance (CL/F)

(AZD9291 only), apparent volume of distribution, mean residence time (MRT), where possible.

Following the multiple dose part of the study:

Cycle 2 Day 1:

Maximum plasma concentration at steady state ($C_{ss max}$), time to $C_{ss max}$ ($t_{ss max}$), minimum plasma concentration at steady state ($C_{ss min}$), area under the plasma concentration-time curve from zero to the end of the dosing interval (AUC_{ss}), apparent plasma clearance at steady state (CL_{ss}/F) (AZD9291 only), extent of accumulation on multiple dosing (R_{AC}), time dependency of the pharmacokinetics.

Cycle 1 Day 8:

CC1D8 max, tC1D8 max, CC1D8 min, AUCtau.

Trough concentrations on Cycle 1 Day 8, day 15 and Cycle 2 day 1.

The ratio of metabolite to AZD9291 will also be calculated.

The maximum plasma concentration (C_{max}), the C_{max} at steady state ($C_{ss max}$), the time of maximum concentration (t_{max}) and the t_{max} at steady state ($t_{ss max}$) will be determined by inspection of the concentration-time profiles. Where possible the terminal elimination rate constant (λ_{z}) will be calculated by log-linear regression of the terminal portion of the concentration-time profiles where there are sufficient data and the terminal half-life $(t_{\nu_{\lambda}z})$ will be calculated as $\ln 2/\lambda_z$. The area under the concentration-time curve up to the last quantifiable sample (AUC_(0-t)) and the area under the concentration-time curve up to 24 hours (AUC₍₀₋₂₄₎) will be calculated using the linear up log down trapezoidal rule. Where appropriate, the AUC(0-t) will be extrapolated to infinity using λz to obtain AUC. The area under the concentration-time curve across the dosing interval, AUCss will be calculated using the linear up log down trapezoidal rule. The apparent clearance (CL/F following the single dose and CLss/F following multiple dosing) will be determined from the ratio of dose/AUC or dose/AUCss. The volume of distribution (Vss/F or Vz/F) will be determined from the mean residence time (MRT) x CL/F and/or the accumulation ratio (RAC) will be calculated as the ratio of the AUC(0-24) on Cycle 2 Day 1 and Cycle 0 Day 1. The time dependency of the pharmacokinetics on multiple dosing will be assessed by the calculation of the ratio of AUC(0 -24) Cycle 2 day 1/AUC Cycle 0 Day 1.

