AZD9291 is an oral, potent, selective, irreversible inhibitor of both EGFR-TKI sensitising and T790 mutations in NSCLC with a significant selectivity margin over wild-type EGFR. AZD9291 will be administered orally as a tablet once a day. A cycle of treatment is defined as 21 days of once daily AZD9291 treatment.

On clinic days on which PK samples are scheduled to be taken, the dosing should be delayed until arrival at the clinic and until the pre-dose ECG has been performed followed by the pre-dose PK sample. Patients should not take their dose until instructed to do so by site personnel.

Duration of treatment

Patients in both cohorts (40 mg and 80 mg once daily) may continue on treatment with AZD9291 until a treatment discontinuation criterion is met. There is no maximum duration of treatment as patients may continue to receive AZD9291 beyond RECIST 1.1 defined progression as long as they are continuing to receive clinical benefit, as judged by the investigator (see Section 5.2).

Outcomes variable(s)

Primary endpoints/variables

PK exposure parameters derived from plasma concentrations of AZD9291, and metabolites AZ5104 and AZ7550.

Following the single dose part (or first dose) of the study:

Maximum plasma concentration (C_{max}), time to Cmax (t_{max}), terminal rate constant (λz), terminal half life ($t_{\nu_{2}\lambda z}$), area under the plasma concentration-time curve from zero to 24 hours (AUC₍₀₋₂₄₎), from zero to 72 hours (AUC₍₀₋₇₂₎), from zero to the time of the last measurable concentration (AUC_(0-t)) and from zero to infinity (AUC), apparent plasma clearance (CL/F) (AZD9291 only), apparent volume of distribution (AZD9291 only), mean residence time (MRT), where possible.

Following the multiple dose part of the study:

Cycle 2 Day 1

Maximum plasma concentration at steady state ($C_{ss max}$), time to $C_{ss max}$ ($t_{ss max}$), minimum plasma concentration at steady state ($C_{ss min}$), area under the plasma concentration-time curve from zero to the end of the dosing interval (AUCss), apparent plasma clearance at steady state (CL_{ss}/F) (AZD9291 only), extent of accumulation on multiple dosing (R_{AC}), time dependency of the pharmacokinetics where possible.

Cycle 1 Day 8

C_{C1D8 max}, t_{C1D8 max}, C_{C1D8 min}, AUC_{tau}

Trough concentrations on Cycle 1 Day 8, day 15 and Cycle 2 day 1.

The ratio of metabolite to AZD9291 will also be calculated.

Secondary endpoints/variables

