AUC _{ss}	Area under plasma concentration-time curve during any dosing interval at steady state [amount time/volume]
CL/F	Total body clearance of drug from plasma after an oral dose
CL _{ss} /F	Total body clearance of drug from plasma after an oral dose at steady state
C _{max}	Maximum plasma concentration
CR	Complete response
CRF	Case Report Form (electronic/paper)
CSP	Clinical Study Protocol
C _{ss,max}	Maximum (peak) steady state drug concentration in plasma during dosing interval [amount/volume]
C _{ss,min}	Minimum (trough) steady state drug concentration in plasma during dosing interval [amount/volume]
CSR	Clinical Study Report
СТ	Computerised tomography
CTCAE	Common Terminology Criteria for Adverse Events
DLT	Dose-limiting toxicity
ECG	Electrocardiogram
Echo	Echocardiogram
EGFR	Epidermal growth factor receptor
EGFRm+	Epidermal growth factor receptor sensitising mutation positive
GCP	Good Clinical Practice
HIV	Human immunodeficiency virus

Abbreviation or special term	Explanation
IATA	International Air Transport Association
ICH	International Conference on Harmonisation
KRAS	v-Ki-ras2 Kirsten rat sarcoma viral oncogene homolog
LIMS	Laboratory Information Management System
LVEF	Left ventricular ejection fraction
MedDRA	Medical Dictionary for Regulatory Activities
MRI	Magnetic resonance imaging
MRT	Mean residence time
MTD	Maximum tolerated dose
MUGA	Multi gated acquisition scan
NE	Not evaluable
NSCLC	Non-small Cell Lung Cancer
NTL	Non-target lesion
OAE	Other significant adverse event
ORR	Objective response rate
PD	Progression of disease
PFS	Progression free survival
РК	Pharmacokinetics
PR	Partial response
QT	ECG interval measured from the onset of the QRS complex to the end of the T wave
QTc	QT interval corrected for heart rate
RBC	Red blood cell
RECIST	Response Evaluation Criteria in Solid Tumours
SAE	Serious adverse event (see definition in Section 6.4.2)
SD	Stable disease
λ_{z}	Smallest (slowest) disposition (=hybrid) rate constant [time-1]
t _{1/2}	Half-life
$t_{\nu_2\lambda_Z}$	Half-life associated with terminal slope (λz) of a semi-logarithmic concentration-time curve [time]
TL	Target lesion
TKI	Tyrosine kinase inhibitor

Abbreviation or special term	Explanation
t _{max}	Time to maximum plasma concentration
t _{ss max}	Time to maximum plasma concentration at steady state
ULN	Upper limit of normal
V_{ss}/F	Volume of distribution (apparent) at steady state after an oral dose
WBDC	Web Based Data Capture
WHO	World Health Organisation
~	Approximately

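### The volume sentence in Section 7.4 is broken: its only formula, MRT × CL/F, is not Vz/F, and after oral dosing it overstates Vss/F

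*Protocol*

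**What the plan says.** The Synopsis and Section 7.1 both list volume among the primary variables of the single-dose part: "apparent volume of distribution (AZD9291 only), mean residence time (MRT), where possible". Section 7.4 gives the rule for calculating it: "The volume of distribution (Vss/F or Vz/F) will be determined from the mean residence time (MRT) x CL/F". What follows is not a coherent sentence: "MRT) x CL/F and/or the accumulation ratio (RAC) will be calculated as the ratio of the AUC(0-24", and so on into the accumulation ratio R_AC.

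The neighbouring text in Section 7.4 matters for reading this:

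- Clearance: "The apparent clearance (CL/F following the single dose and CLss/F following multiple dosing) will be determined from the ratio of dose/AUC or dose/AUCss".
- The terminal rate constant λz "will be calculated by log-linear regression of the terminal portion of the concentration-time profiles where there are sufficient data".
- General method: "PK parameters will be derived using standard non-compartmental methods". MRT is not defined further, and no correction for absorption time is mentioned.

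The Synopsis states the route: "AZD9291 will be administered orally as a tablet once a day". No intravenous reference dose is described. The abbreviation list has an entry for Vss/F, "Volume of distribution (apparent) at steady state after an oral dose", without a formula, and no entry for Vz/F. Section 7.7 and the Synopsis summarise a single volume of distribution without saying which one.

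Section 7.4 introduces its parameter list as applying to AZD9291, AZ5104 and AZ7550. It limits CL/F to AZD9291 but, unlike Section 7.1 and the Synopsis, does not limit volume.

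**The concern.** Two different volumes are named and one expression is printed. That expression is not the identity for Vz/F. It is the identity for Vss/F only when MRT is the disposition (intravenous) value, which an oral-only study does not observe. Someone following the printed rule would therefore report an upward-biased Vss/F, or a number labelled Vz/F that is something else. Because the summary tables name only a volume of distribution, a reader of the report could not tell which was meant.

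The missing AZD9291-only limit adds a small contradiction. For the metabolites, MRT × CL/F cannot be formed under the section's own rules, because CL/F is not derived for them.

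**Working it through.** The protocol states no figure on this point, so there is none to reproduce.

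**Identities**

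- Vz/F = (CL/F)/λz = Dose/(λz × AUC).
- Vss/F = MRT_iv × CL/F.
- After an oral dose, AUMC/AUC = MRT_oral = MRT_iv + MAT.
- Hence MRT_oral × CL/F = Vss/F + MAT × CL/F. The excess is positive whenever absorption takes time.

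**Size of the excess in Vss/F, one compartment**

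The relative excess is λ × MAT = ln 2 × MAT / half-life. The protocol gives neither a half-life nor an absorption rate, so both are assumed.

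| Half-life (assumed) | MAT 2 h | MAT 8 h |
|---|---|---|
| 36 h | 0.693 × 2/36 = 3.9% | 0.693 × 8/36 = 15.4% |
| 48 h | 0.693 × 2/48 = 2.9% | 0.693 × 8/48 = 11.6% |
| 72 h | 0.693 × 2/72 = 1.9% | 0.693 × 8/72 = 7.7% |

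The range is about 2% to 15%.

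**Wider range**

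Here the assumed half-life is 12 to 72 h and the assumed absorption half-life 0.5 to 4 h (MAT = absorption half-life / ln 2, so 0.7 to 5.8 h). The two-compartment model uses assumed k12 = k21 = 0.1/h.

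| Ratio | One compartment | Two compartments |
|---|---|---|
| MRT_oral × CL/F to true Vss/F | 1.01 to 1.33 | 1.01 to 1.56 |
| MRT_oral × CL/F to true Vz/F | 1.01 to 1.33 | 0.64 to 1.01 |

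The largest one-compartment value is 1 + 4/12 = 1.33. Within this grid, half-lives of 36 to 72 h give an excess over Vss/F of about 1% to 12%. Against Vss/F the error is always upward. Against Vz/F it can go either way.

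**Does the alternative work on this study's samples?**

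Noise-free profiles from the same models were evaluated at the single-dose times in Table 4 (last sample 120 h). AUC used the linear up log down rule with extrapolation, and λz came from the last three points. (CL/F)/λz returned 0.99 to 1.02 times the true Vz/F throughout.

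**The case against.** The strongest objection concerns the damaged sentence. A reader who stops at CL/F might infer that the plan prescribes MRT × CL/F for Vz/F. The text does not establish that. The and/or cannot sensibly join a volume formula to the definition of R_AC, so a second volume expression and a sentence break seem to have dropped out. The preceding sentence pairs two clearances with two ratios; read the same way, MRT × CL/F would belong to Vss/F and the formula for Vz/F would be the missing one. Section 7.4 also invokes standard non-compartmental methods and derives both quantities that Vz/F needs. This objection stands, and it limits the point on Vz/F to the absence of a legible formula. It does not rescue Vss/F: the MRT × CL/F expression is complete and, with MRT as AUMC/AUC, biased upward whatever followed it.

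A reader might also infer that comparison of volumes with other AZD9291 studies is lost. The documents do not support this. They do not show how other studies calculated volume, the primary objective is to characterise PK in Chinese patients, and the only cross-study expectation, in Section 5.3, concerns exposure.

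It can fairly be said that the Vss/F excess is modest if elimination is slow, and that the abbreviation list already calls the quantity apparent and after an oral dose. That bears on severity. It does not state the absorption bias. Nor can the matter simply be left to a statistical analysis plan, since the protocol itself prints the formula.

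**Conclusion.** The point holds as a defect in wording with a modest numerical consequence. Section 7.4 gives no legible formula for Vz/F, and the one expression it does give overstates Vss/F after oral dosing. The direction is certain if MRT is the usual AUMC/AUC. The size rests on assumed values: about 2% to 15% for MAT 2 to 8 h and half-life 36 to 72 h, and up to 33% (one compartment) or 56% (two compartments) at an assumed half-life of 12 h with an absorption half-life of 4 h. If MRT × CL/F were reported as Vz/F, which is not shown to be intended, the ratio to the true value would lie between 0.64 and 1.33 in the ranges examined.

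Severity is minor to moderate. Volume is a listed primary variable, but it is one of many summarised descriptively in about 12 patients per cohort, no test or decision rule is tied to it, and AUC, Cmax and CL/F do not depend on it.

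**What to change.** In Section 7.4:

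1. State the reported volume as Vz/F = (CL/F)/λz = Dose/(λz × AUC), for AZD9291 only, after the single dose.
2. Drop Vss/F. Alternatively, keep it with a statement that oral MRT includes absorption time, which cannot be separated without intravenous data, so that MRT × CL/F overestimates Vss/F.
3. Define R_AC in its own sentence.
4. Add the AZD9291-only limit to volume in the parameter list, to agree with Section 7.1 and the Synopsis.

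Use the same label in the summary lists of Section 7.7 and the Synopsis, and in the abbreviation list. The cost is a few lines of text. No new samples or data are needed, because λz, AUC and CL/F are already to be derived.
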